9.2 POPULATIONS FOR ANALYSES

The population for this study is defined separately by molecular cohort and disease severity (tdMeta and μ Meta). The study includes participants diagnosed with both ctDNA positive recurrence, and those who are traditionally defined metastatic, relapsed, refractory, or advanced stage III or IV solid tumors that meet the entry criteria for one of the biomarker cohorts. In addition, subgroup analyses may be conducted to assess antitumor activity in cohorts of participants defined by the multiple molecular markers.

The analysis populations are defined in **Table E** according to cohort and disease severity.

Table E: Populations for Analyses

Population	Description
As-treated Population	All participants who receive at least 1 dose of assigned therapy
Intent-to-treat (ITT) Population	All participants who provide written informed consent and are assigned therapy
Modified ITT (mITT) Population	All participants belonging to the ITT Population who receive at least 1 dose of assigned therapy and 1 post-baseline scan

The information contained in this protocol and all other information relevant to this study are confidential and proprietary information of Strata Oncology Inc., except as may be required by federal, state or local laws or regulation, and may not be disclosed to others without prior written permission of Strata.

Page 46 of 56

9.3 STATISTICAL ANALYSES

9.3.1 GENERAL APPROACH

This study will use an adaptive approach, with on-treatment data guiding trial adaptation and success or futility of each cohort. All statistical analyses will be pre-specified and finalized for each cohort prior to database lock. The statistical analysis plan (SAP) will describe the study populations to be included in the analyses and the procedures for accounting for missing, unused, and spurious data. High-level methods are described here.

9.3.2 EFFICACY ANALYSES

Efficacy analyses for ORR and DoR are based on the responses from Investigator-recorded measurements and assessments for target, nontarget, and new lesions according to RECIST 1.1.²¹

- ORR is defined as the percentage of participants with a best overall response of complete response (CR) or partial response (PR).
- DoR is defined as the time from first documentation of disease response (CR or PR) until first documentation of progressive disease.

Efficacy analyses for ctDNA response rate will be based on the proportion of participants considered responders compared to non-responder participants. Responders are defined as any participant with <50% ratio of mean VAF.

ORR and ctDNA response rate will be estimated by the proportion of participants with objective response and ctDNA response respectively and their 95% confidence intervals will be estimated using the exact binomial method. Other time-to-event efficacy analyses including TTD, TTNT, DFS and OS will be summarized using the Kaplan-Meier method with the appropriate time-defined cut-offs.

Additional supportive analyses of efficacy endpoints may be conducted using iRECIST.²²

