3 OBJECTIVES AND ENDPOINTS

3.1 OBJECTIVES AND ENDPOINTS

All endpoints will be assessed independently for each biomarker-defined cohort. **Tables A and B** list the objectives and endpoints for this study. Cohorts are stratified based on disease

The information contained in this protocol and all other information relevant to this study are confidential and proprietary information of Strata Oncology Inc., except as may be required by federal, state or local laws or regulation, and may not be disclosed to others without prior written permission of Strata.

Page 19 of 56

severity: (1) traditionally defined metastatic/advanced (tdMeta), and (2) micro-metastatic (μ Meta).

Table A: StrataPATH Objectives and Endpoints for tdMeta Cohorts

tdMeta Cohorts	
OBJECTIVES	ENDPOINTS
Primary	
Assess the clinical activity of anti-cancer therapies in participants with pre-specified biomarker profiles.	ORR – Overall Response Rate is defined as the percentage of participants with a best overall response of CR or PR based on Response Evaluation Criteria in Solid Tumors (RECIST) 1.1, as assessed by the investigator.
Secondary	
Assess the duration of response in anti-cancer therapies in participants with pre-specified biomarker profiles.	
 DoR – Duration of response is defined as the time from first documentation of disease response (CR or PR) until first documentation of progressive disease. TTD – Time to treatment discontinuation is defined as length of time from the date the participant initiates the systemic treatment to the date the participant discontinues treatment TTnT – Time to next treatment is defined as the length of time from the date the participant initiates study treatment to the date the participant initiates their next systemic treatment or death.
Evaluate ctDNA response rate at timepoints for participants who received anti-cancer therapies with pre-specified biomarker profiles.	ctDNA response – Proportion of participants with a <50% ratio of mean VAF will be defined as ctDNA responders. Molecular response is calculated as a ratio of mean VAF on-treatment at different timepoints compared to their baseline VAF.
Evaluate overall survival (OS) for participants who received an anticancer therapy with pre-specified biomarker profiles.	OS – Time from initiation of treatment until death from any cause.
Monitor and characterize the overall safety in the biomarker cohorts	The incidence of serious adverse events (SAEs).
Exploratory	

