Explore the relationship between serial ctDNA measurement and participant response to therapy.	N/A

Table B: StrataPATH Objectives and Endpoints for μ Meta Cohorts

μ Meta Cohorts

The information contained in this protocol and all other information relevant to this study are confidential and proprietary information of Strata Oncology Inc., except as may be required by federal, state or local laws or regulation, and may not be disclosed to others without prior written permission of Strata.

Page 20 of 56

OBJECTIVES	ENDPOINTS
Primary	
Evaluate ctDNA response rate at 6 months for participants who received an anticancer biomarker-guided therapy.	ctDNA response – Proportion of participants with a <50% ratio of mean VAF will be defined as ctDNA responders. Molecular response is calculated as a ratio of mean VAF on-treatment at 6 months compared to their baseline VAF.
Secondary	
Evaluate the ctDNA response rate at additional timepoints for participants who receive an anticancer biomarker therapy.	ctDNA response – Proportion of participants with a <50% ratio of mean VAF will be defined as ctDNA responders. Molecular response is calculated as a ratio of mean VAF on-treatment at additional timepoints compared to their baseline VAF.
Evaluate Disease-Free Survival (DFS) stratified by ctDNA status or response at different timepoints.	DFS – Time from initiation of treatment until disease recurrence or death from any cause.
Assess the correlation between ctDNA and Disease-Free Survival (DFS).	DFS – Time from initiation of treatment until disease recurrence or death from any cause.
Evaluate overall survival (OS) for participants who received an anticancer biomarker-guided therapy.	OS – Time from initiation of treatment until death from any cause.
Monitor and characterize the overall safety for participants in the biomarker cohorts	Incidence of serious adverse events (SAEs).

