4 STUDY DESIGN

4.1 OVERALL DESIGN

Participants who are 18 years of age or older, have been diagnosed with histologically documented solid tumors, have an eligible biomarker profile, and are planned for treatment may be eligible for this study according to the criteria in **Sections 5.1-5.2** and the supplemental criteria in the specific biomarker/drug cohort appendix.

Each biomarker/drug cohort will be described in an appendix to this study protocol. Appendix information includes investigational product overview, rationale for biomarker/drug combination, additional cohort-specific eligibility criteria, study treatment including dosing and administration guidelines, along with known adverse reactions.

After obtaining informed consent, study staff shall assess individual participant eligibility using the criteria in **Sections 5.1-5.2** and the supplemental criteria in the specific appendix they are targeting for enrollment. The designated study staff will enter the participant's details into the electronic data capture (EDC) to support a sponsor-required confirmation of biomarker eligibility. Upon confirmation of eligibility and informed consent procedures, the participant will be formally enrolled into the study. Participants will be treated with the applicable cohort's study drug according to dosing instructions in the approved product labeling or provided Investigator's Brochure (IB).

For participants who exhibit more than 1 eligible biomarker result, the treating physician should determine the most appropriate cohort assignment. Factors for consideration include the drug's dosing and administration guidelines, as well as the commercially available product prescribing instructions or provided IB.

A leftover tumor specimen (if historical comprehensive genomic profiling (CGP) and/or ribonucleic acid (RNA) profiling results are not available for submission) and blood sample for ctDNA analysis will be collected at study entry (prior to therapy start). Blood samples will be

The information contained in this protocol and all other information relevant to this study are confidential and proprietary information of Strata Oncology Inc., except as may be required by federal, state or local laws or regulation, and may not be disclosed to others without prior written permission of Strata.

Page 23 of 56

collected and CT/MRI scans will be performed until treatment discontinuation as outlined in the Study Schedule of Activities (SOA) (**Section 7.2**).

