7 STUDY PROCEDURES AND SCHEDULE

7.1 STUDY PROCEDURES

7.1.1 STUDY SPECIFIC PROCEDURES

All procedures listed here are specific to the study and are not part of standard clinical care:

- Review and sign informed consent
- Eligibility criteria review
- Biological specimen collection
 - Two 10 milliliter (mL) tube of blood (20 mL total) will be collected via venipuncture
- Archival FFPE tissue submission (if historical CGP and/or Strata RNA profiling results are unavailable or as otherwise indicated within the cohort-specific criteria)
- Biomarker confirmation (biomarker test results)
- Data collection of any standard of care procedures conducted as part of regular clinical visits
- Study drug dispensing
- Study drug administration
- CT/MRI scan of abdomen, chest, and pelvic area
- Tumor assessments (RECIST 1.1 or iRECIST)
- Drug administration and accountability
- Evaluation and documentation of adverse events (AEs) or serious adverse events (SAEs)
- Electrocardiograms (EKGs) and/or echocardiogram (Echo) are required for eligibility determination at screening. If not done as part of standard of care work-up or historical

The information contained in this protocol and all other information relevant to this study are confidential and proprietary information of Strata Oncology Inc., except as may be required by federal, state or local laws or regulation, and may not be disclosed to others without prior written permission of Strata.

Page 30 of 56

EKG and/or Echo are not available, these tests should be performed as research procedures.

- A serum pregnancy test is required if the pre-treatment urine pregnancy test is positive or inconclusive. Pregnancy tests must be documented as negative within 3 days of study treatment.

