7.2.1 SCHEDULE OF ACTIVITIES

The schedules of activities (SOA) for both the tdMeta and μMeta cohorts are detailed in **Table C** and **Table D**. StrataPATH is designed to mimic real-world practice and will have a limited number of study-specific visits (**Section 7.1**). The visit schedules are comprised of a combination of study-specific visits and standard of care (SOC) visits. Participants will be followed for up to 3 years from the time of consent.

SOC procedures listed in the SOA typically occur during standard clinical visits and are to be documented within the EDC system at the timepoints outlined in the SOA.

The information contained in this protocol and all other information relevant to this study are confidential and proprietary information of Strata Oncology Inc., except as may be required by federal, state or local laws or regulation, and may not be disclosed to others without prior written permission of Strata.

Page 32 of 56

Table C: StrataPATH Schedule of Activities – tdMeta Cohorts

SCHEDULE OF ACTIVITIES STR-004-001: StrataPATH tdMeta Cohorts	STUDY VISITS (participation up to 3 years)			
	Screening	Baseline	On Treatment	Post-Treatment ^g
Study Procedures				
Review and Sign Informed Consent Form	X			
Eligibility Criteria Review (Main and Cohort-Specific)	X	X		
Biomarker Confirmation	X			
CT Scan or MRI of Abdomen, Chest, and Pelvic Area		X ^a	X ^{b,c}	
RECIST 1.1 (or iRECIST) Assessment		X	X ^{b,c}	
Blood Draw: Whole Blood		X	X ^{b,c}	
FFPE Tissue Collection	X ^d			
Study Drug Administration		X ⁱ	X ⁱ	
Study Drug Accountability		X	X	X ^h
Study Drug Discontinuation				X ^h
Standard of Care (SOC) Procedures^e				
Documentation of Biomarker Results	X ^e			
Demographics	X ^e			
Medical History	X ^{e,f}		X ^e	X ^e
Cancer Diagnosis	X ^e			
Prior and Concomitant Medications	X ^{e,f}		X ^e	X ^e
Physical Exam (Complete or Abbreviated)	X ^e		X ^e	X ^e
ECOG Performance Status	X ^e	X ^e	X ^e	X ^e
Height, Weight, Vital Signs	X ^e		X ^e	X ^e
Electrocardiogram (EKG)	X ^j		X ^e	X ^e
Echocardiogram (Echo)	X ^j			
Hematology	X ^e		X ^e	X ^e
Serum Chemistry	X ^e		X ^e	X ^e
Urine Pregnancy Test, Serum Pregnancy Test ^k	X ^e	X ^e	X ^e	
Safety Evaluation				
Adverse Events/Serious Adverse Events		X	X	X

^aIf a scan was performed within 28 days of the baseline visit, these results should be submitted to the study.

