7.2.2.4 POST-TREATMENT

Study drug will be discontinued upon disease progression or based on physician's discretion as described in **Section 5.5**. Site staff should collect unused study drug and any empty packaging and perform drug accountability upon study drug discontinuation. Participants that discontinue drug will remain on study for 3 years from the date of informed consent for follow-up data entry purposes only. No additional study specific procedures will occur following discontinuation. Participants will continue to see their physician for SOC clinic visits. Site staff will be responsible for collecting and entering the information below in EDC from the participants SOC clinic visits every 3 months.

- Medical history (specifically, disease recurrence and/or survival status)
- Concomitant medications (specifically, anticancer therapies)
- Standard of care procedures, including ECOG status

7.2.3 μMETA COHORTS

Note that μMeta cohorts will not have CT/MRI scans or RECIST 1.1 (or iRECIST) assessments performed.

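### Duration of response ends only at documented progression, so a responder's death without it is never an event; and the protocol contradicts itself on tumour assessments after drug stops for other reasons

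*Protocol*

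**What the plan says.** The protocol defines duration of response (DoR) twice, identically. Table A in 3.1 has "time from first documentation of disease response (CR or PR) until first documentation of progressive disease", and 9.3.2 has "DoR is defined as the time from first documentation of disease response (CR or PR) until first documentation of progressive disease". Neither mentions death. Two other endpoints in 3.1 do: time to next treatment (TTnT) runs until the participant "initiates their next systemic treatment or death", and disease-free survival runs "until disease recurrence or death from any cause".

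On imaging after study drug stops, the protocol gives two rules.

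- **Scans end with drug.** Section 4.1 says "CT/MRI scans will be performed until treatment discontinuation". Table C in 7.2.1 marks the row "CT Scan or MRI of Abdomen, Chest, and Pelvic Area" at baseline and on treatment and leaves the post-treatment column blank; its footnote b sets the timing on treatment. Section 7.2.2.4 says "No additional study specific procedures will occur following discontinuation", and 7.1.1 lists "CT/MRI scan of abdomen, chest, and pelvic area" and tumour assessments among the study-specific procedures.
- **Scans continue.** The third paragraph of 7.3.1 keeps tumour assessments going for participants who stop drug for reasons other than progression, until death, progression, new systemic therapy or another listed end point. Section 6.4 also says that remaining procedures are to be completed whether or not the participant is on treatment.

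The first sentence of 7.3.1 states both rules at once: assessments run to progression irrespective of treatment, or until the participant stops drug.

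**The concern.** A response that ends in death has ended. Under the written definition it has not: that participant has no event and, in a Kaplan-Meier analysis, can only be censored. Censoring at death treats the participant as someone who might still be in response later, so the estimated curve lies on or above the one for progression or death. DoR is the first-listed secondary endpoint for the tdMeta cohorts and is what a reader uses to judge whether a single-arm response rate is worth anything. With few responders per cohort, one or two such deaths matter.

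The imaging conflict adds to this. If a site stops scanning when drug stops, later progression in a responder may never be documented by a protocol RECIST assessment; if another site continues, it will be. The same endpoint would then be observed differently across sites.

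**Working it through.** **Step 1, the text.** No figure in the protocol bears on DoR, so there is nothing to reproduce. Side by side:

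| Endpoint | Place | Death an event? |
|---|---|---|
| DoR | 3.1 Table A; 9.3.2 | No |
| TTnT | 3.1 Table A | Yes |
| DFS | 3.1 Table B; 3.2.3 | Yes |

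Section 9.3.1 leaves analysis populations and the handling of missing, unused and spurious data to the SAP. It does not leave endpoint definitions there. An SAP that counted death would have to depart from the protocol.

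**Step 2, size of the definition gap.** Assume constant hazards and a share f of response endings that are deaths without documented progression. Let M be the median time to progression or death.

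- Total hazard: H = ln 2 / M. Progression hazard: h = H(1-f).
- Median with such deaths censored: ln 2 / h = M/(1-f).
- Proportion in response at 12 months: exp(-12H) against exp(-12h).

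With M = 8.0 months, exp(-12H) = 0.354, and:

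| f | Factor 1/(1-f) | Progression-only median (months) | 12-month proportion |
|---|---|---|---|
| 10% | 1.11 | 8.89 | 0.392 |
| 20% | 1.25 | 10.00 | 0.435 |
| 30% | 1.43 | 11.43 | 0.483 |

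At f = 5% the factor is 1/0.95 = 1.05.

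**Step 3, how often it would arise.** Section 9.1 rejects the null with 6 or more responses in 35, and 30% of 35 is about 10. The chance of at least one such death among n responders is 1-(1-f)^n:

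- n = 6: 0.469, 0.738, 0.882 for f = 10%, 20%, 30%.
- n = 10: 0.651, 0.893, 0.972.

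This assumes every response is followed to its end. Follow-up stops at 3 years from consent, so these are upper bounds.

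**Step 4, the imaging conflict.** Set the on-drug progression hazard to 1. Let q be the share of responders who stop drug before progression, so the stopping hazard is s = q/(1-q); q = 0.2 gives s = 0.25. Let k be the off-drug progression hazard. With continued assessment,

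S(t) = exp(-(1+s)t) + ∫₀ᵗ s·exp(-(1+s)u)·exp(-k(t-u)) du.

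With censoring at drug stop the median is ln 2. The ratio of the censored median to the continued-assessment median is:

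| k | 0.5 | 1 | 1.5 | 2 | 3 |
|---|---|---|---|---|---|
| Ratio | 0.952 | 1.000 | 1.036 | 1.064 | 1.105 |

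As a check at k = 2, S(t) = (4/3)exp(-1.25t) - (1/3)exp(-2t). At t = 0.693/1.064 = 0.651 this is 0.591 - 0.091 = 0.500.

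**The case against.** The best defence is that time to documented progression is a coherent, narrower estimand. The two definitions agree with each other, 9.3.2 ties DoR to RECIST lesion assessments, and endpoints may differ in what they count. Table A also puts TTnT, which counts death, under the same duration objective, and OS is a separate endpoint, so deaths are not lost to the trial. This softens the point but does not remove it. TTnT starts at treatment initiation and covers everyone, not responders from first response. Nor does the protocol say that a progression-only DoR is intended or how death is then to be read.

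It is also true that the Kaplan-Meier sentence in 9.3.2 does not name DoR, and the SAP could treat death as a competing event. The complaint is about the event definition, which holds under any method. Keeping the dead in the risk set lengthens the median further: solving (1-f)(1-exp(-Ht)) = 0.5 with a 6-month median gives 6.7/(no censoring: 7.0), 7.5/(8.5) and 8.6/(10.8) months for f = 10%, 20%, 30%, the first figure in each pair being the censored one.

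Precision will be poor with 6 to 10 responders, so an 11% to 43% shift may sit well inside the confidence interval. That limits how visible the bias is; it does not justify fixing it into the definition.

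Two smaller points stand. The imaging effect on DoR is modest and its direction is unknown. The 3-monthly entry of recurrence and survival status under 7.2.2.4, and the option in 4.1 to request further imaging after an efficacy signal, reduce it further without replacing scheduled RECIST assessments. And while the DoR definition leaves ORR alone, the imaging rule might not: whether scans continue after drug stops can decide whether a later response is recorded, or whether a participant has the post-baseline scan that the mITT population in 9.2 requires.

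**Conclusion.** The plan is wrong as written on both counts. DoR omits death from its event definition in both places where it is defined. With deaths censored, the reported curve can only equal or exceed the one for progression or death; under constant hazards the median is longer by 1/(1-f), that is 5% to 43% for f between 5% and 30%. The protocol also gives incompatible instructions on tumour assessments after drug stops for reasons other than progression. With 20% of responders stopping this way, the effect on the median runs from 5% too short to about 11% too long, upward only if progression is faster off drug.

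The values of f, the 6.0- and 8.0-month medians, the 20% and the hazard ratios are assumptions. The textual findings do not depend on them. DoR is secondary, so this should be corrected but does not overturn the primary decision rule.

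**What to change.** In Table A of 3.1 and in 9.3.2, define DoR as the time from first CR or PR to first documented progression or death from any cause, whichever comes first, with participants alive and progression-free censored at their last adequate tumour assessment. If a progression-only measure is truly wanted, name it as such, justify it and state how death is handled.

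Reconcile 4.1, 6.4, Table C with its footnote b, 7.2.2.4 (read with 7.1.1) and both paragraphs of 7.3.1 to a single rule on tumour assessments after drug stops for reasons other than progression. Which rule is for the sponsor to decide. Then match DoR censoring to it, including at the start of new anticancer therapy, where 7.3.1 ends assessments.

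The cost is one definition reworded in two places and one consistency edit. Survival status is already collected under 7.2.2.4, so the definition change needs no new data. Reported DoR will be equal or shorter.
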